Phase I study P188 (NCT03610334, EudraCT 2018-000443-29) was a randomised, double-blind, placebo-controlled, single and multiple ascending dose study to evaluate the safety, tolerability and pharmacokinetics (PK) of IFB-088 when administered to healthy adult subjects. The study consisted of a single ascending dose (SAD) part, and a multiple ascending dose (MAD) part. The study is complete and a total of 72 subjects received IFB-088 or placebo. In the SAD part, 36 subjects received single daily doses of IFB-088 ranging from 2.5 to 60 mg; in the MAD part, 18 subjects received multiple doses of IFB-088 ranging from 15 mg to 50 mg over 14 days. Drug absorption was rapid and maximum concentrations were observed at approximately 1-2 hours (median time at which the C_{max} is observed [T_{max}]) following single and multiple oral dose administration of IFB-088. Dose proportionality was observed for IFB-088 C_{max} and AUC following single daily doses of 10 to 60 mg and multiple daily doses of 15 to 50 mg for 14 days. IFB-088 half-life was 4.6 to 6.2 hours following single doses and 5.7 to 8.4 hours following multiple dosing. The terminal elimination half-lives were similar between Days 1 and 14, suggesting the stationarity (time-independence) of the IFB-088 PK over 14 days. Following repeated bi-daily administration, the drug accumulation ratio ranged between 1.4 and 1.6. Very low concentrations of IFB-088 were evident in urine; the percentage of the administered dose excreted unchanged in urine was < 1%. The primary metabolic pathway proposed in nonclinical studies included the oxidation of IFB-088 to IFB-139 (phase I metabolite) followed by glucuronidation (phase II metabolite), and was confirmed in the P188 study. Based on the population PK model, renal clearance likely marginally contributes to IFB-088 total clearance, while the formation of metabolite IFB-139 by hydroxylation has a major contribution to IFB-088 elimination.

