The safety results from the phase I study are reassuring and no serious adverse reactions are considered expected by the sponsor for the purpose of expedited reporting of suspected unexpected serious adverse reactions (SUSARs). However, human safety data with IFB-088 are limited to the results of this first-in-human study on healthy volunteers. Since IFB-088 has never yet been tested in ALS patients, who may present with potential additional risk factors linked to their condition, a set of measures will be implemented in this study in order to minimise those potential risks, including i) Restriction of eligibility criteria to patients with no other serious illness(es) or medical condition(s) such as cancer, cardiac, liver, renal or haematological diseases, ii) Regular monitoring of safety laboratory and clinical AEs in all patients enrolled in the present clinical trial, since as with any new drug, there is a risk that unidentified or unexpected side effects may occur, iii) Definition, monitoring and specific reporting procedure for AEs of special interest (AESIs), iv) Implementation of a data safety monitoring board (DSMB) for periodic benefit risk assessment.

In preclinical studies, kidneys appeared to be the only affected organs in Sprague Dawley rats at IFB-088 doses above the NOAEL (1.5 mg/kg/b.i.d., i.e. 3 mg/kg/day). Adverse, dose-related crystal nephropathy was observed in both sexes, but at slightly lower doses in males compared to females and was the first cause of moribundity and death. No signs of crystal nephropathy were reported in dogs and rabbits at dose levels of up to 16 mg/kg/day (i.e. 8 mg/kg b.i.d.) and 24 mg/kg/day (i.e. 12 mg/kg b.i.d), respectively. In the phase I P188 study no changes in the renal-associated biochemistry parameters and no IFB-088 related AEs from the renal system organ class were reported. Although the renal findings in the Sprague Dawley rat strain are not completely understood yet, the current data suggest that it likely represents a species-specific toxicity not representative of the risk in humans. Nonetheless renal toxicities will be reported in this study as AESIs and renal function will be closely monitored, along with microscopic examination of urine to detect crystals.

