4.1.4 V2 visit

The V2 visit will occur 4 weeks after V0 (\pm 4 days).

The day before V2 the patient will go on site to be administered the IMP at 20:00. The day of V2 the patient must be present on site around 7:30 as a blood sample for PK will be collected in the morning of V2 before the IMP administration that will take place at 08:00. Patients can, but are not forced to, spend the night at the site between these 2 drug administrations, upon agreement between both parties. Patients who leave far away from the investigational site and cannot be hospitalized during the night before V2 for logistical reasons are allowed to take the evening study treatment at home on the day before V2. In this case, the time of dosing must be set by the study team, depending on the time of planned first PK blood sampling at V2, allowing a 12-hour interval between last drug intake and blood sampling. If the patient cannot take the drug at the exact time requested by the hospital, he must note the actual time of drug intake. Patients who do not spend the night in the hospital must be provided with a sterile container to collect morning urine. It will be given to the patient at V1 for those who will not come to the hospital for drug administration on the day before V2.

The following assessments will be conducted at V2:

- Physical examination and vital signs assessment, according to [Sections 4.2.1.2](#) and [4.2.1.5](#),
- Weight and calculation of BMI,
- 12-lead ECG ([Section 4.2.1.6](#)),
- Blood and urine sample collection for haematology, blood chemistry, urinary analysis according to [Section 4.2.1.8](#),
- Crystalluria analyses according to [Section 4.2.1.9](#),
- PK blood samples collection according to [Section 4.2.2.2](#),

- Query for changes in concomitant medications,
- Recording of AEs (if any),
- Pregnancy test in WOCBP. In addition to tests performed at hospital visits, pregnancy tests will be performed at monthly intervals during treatment and until the end of relevant systemic exposure. If a positive result is detected with urine pregnancy test, a serum pregnancy test will be performed to confirm the results.
- Dispensation of study product to the patient,
- Appointment for the next visit,
- Patients will be given a prescription for blood sampling (creatininemia and eGFR) to be performed at V2 + 1 month in a local laboratory. Results of these analyses will be sent to the site in real time,
- eCRF recording of data collected.

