4.1.8 FU visit – V-FU

The V-FU will occur 4 weeks (\pm 1 week) after V4.

The following assessments will be conducted:

- Physical examination and vital signs assessment, according to [Sections 4.2.1.2](#) and [4.2.1.5](#),
- Weight and calculation of BMI,
- 12-lead ECG ([Section 4.2.1.6](#)),
- Crystalluria analyses according to [Section 4.2.1.9](#),
- Blood and urine samples collection for haematology, blood chemistry, and urinary analysis according to [Section 4.2.1.8](#),
- Serum pregnancy test,

⁸ The sniff test is optional. It will be performed only in sites that have the equipment and resources to perform this test.

- Query for changes in concomitant medications,
- Recording of AEs (if any),
- eCRF recording of data collected.

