According to section 4.4 of riluzole SmPC, ALT should be measured every month during the first 3 months of treatment, every 3 months during the remainder of the first year, and periodically thereafter. This monitoring should be performed more frequently in patients with ALT increase under treatment. Depending on the date when riluzole has been initiated and the kinetics of ALT, additional measurements of ALT might therefore be necessary.

Urinary analysis

It includes blood, leukocytes, pH, glucose, and proteinuria assessed by means of commercial urine dipsticks. In case of proteinuria ≥ 30 mg/dL on the dipstick, 24-hour protein is also performed.

Urinary analysis will also include measurement of beta 2 microglobuline or albumin-to-creatinine ratio in mg/g or mg/mmol, microalbumine, creatinine, and proteins, and cytobacteriological examination of urine (CBEU). All these analyses will be performed in a spot urine sample.

4.2.1.9 *Crystalluria*

Microscopic analysis of urine will be performed to investigate drug-related crystalluria. Sample of first-morning micturition will be collected at the V2 visit. The sample will be collected by the hospital staff if the patient has been hospitalised the day before (see [Section 4.1.4](#)), or by the patients themselves if they have spent the night outside the hospital. In this case, patients will receive a sterile dedicated container either on the day before the V2 visit when they go on site for the IMP administration for PK assessment, or at the end of the V1 visit for those who will take the evening treatment at home before V2. A sample of 50 ml will be frozen at -20°C and sent to a central laboratory that will perform microscopic analysis within 7 days after urine collection. Urine freezing should be done within 3h of collection.

Crystalluria will also be investigated at the V-FU visit or at the premature discontinuation visit if any. Urine will be collected when the patient arrives in the hospital for his visit.

4.2.1.10 *Pregnancy testing*

All female patients of childbearing potential will have to perform a blood beta-human chorionic gonadotropin (beta-HCG) testing at screening. For WOCBP, high sensitivity urine pregnancy test will be performed at baseline and repeated on a monthly basis during treatment and until the end of relevant systemic exposure, as well as in case of premature discontinuation and at any time if pregnancy is suspected (sensitivity 25 mIU/ml or more).

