5.12.3.1.8 Crystalluria

Only a listing of crystalluria will be done.

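### In patients who complete treatment, crystal microscopy is scheduled on treatment only once, at week 4 of 26; the next sample comes 3 to 5 weeks after the last dose

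*Protocol*

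**What the plan says.** Protocol 4.2.1.9 gives the purpose: "Microscopic analysis of urine will be performed to investigate drug-related crystalluria". Protocol 1.3 presents it as part of the renal risk mitigation: "renal function will be closely monitored, along with microscopic examination of urine to detect crystals".

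The timing is consistent across the synopsis, Table 2, Table 3 and Sections 4.1.4 to 4.1.9:

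- On treatment: "Sample of first-morning micturition will be collected at the V2 visit", and "The V2 visit will occur 4 weeks after V0" (± 4 days).
- Second examination: "Crystalluria will also be investigated at the V-FU visit or at the premature discontinuation visit if any". "The V-FU will occur 4 weeks" (± 1 week) after V4.
- No crystal microscopy is scheduled at screening, V0, V1, V3, V3bis or V4.

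SAP 5.2.10 dates the last intake of patients who complete treatment at V4. Protocol 1.1.2.2 gives the half-life of IFB-088 as "5.7 to 8.4 hours following multiple dosing". For the analysis, SAP 5.12.3.1.8 says: "Only a listing of crystalluria will be done".

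**The concern.** A test for drug-related crystals is informative when the urine is formed while the drug is present. In completers, only the week-4 sample meets that condition. The V-FU sample is taken well after the drug has gone.

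The stake is the length of exposure covered. Crystal nephropathy was the dose-limiting effect in rats (Protocol 1.1.2.1), and Section 1.3 says the renal findings are not yet fully understood. Repeated dosing in humans had lasted 14 days before this trial. Renal toxicities are an adverse event of special interest (Protocol 7.4), and the incidence of such events belongs to the primary endpoint. The trial extends exposure to 26 weeks, yet for completers its one dedicated crystal test covers only the start of that period.

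Interpretation is harder for two further reasons. There is no baseline examination, so comparison with placebo is the main way to judge whether crystals are drug-related, and the SAP plans no count by arm. The specimens also differ: first-morning urine at V2, urine passed on arrival at V-FU.

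**Working it through.** **The plan's own detection figure.** The documents give none for crystals. The only one is for serious adverse events among 28 active patients (Protocol 8.1.2), from 1 − (1 − p)^28:

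- p = 5%: 1 − 0.95^28 = 76.2%, as stated.
- p = 10%: 1 − 0.90^28 = 94.8%, as stated.

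**Step 1: time off drug at V-FU.** Last intake is at V4 (SAP 5.2.10) and V-FU is 4 ± 1 weeks later (Protocol 4.1.8). Half-lives elapsed = hours ÷ half-life, with the multiple-dose range of 5.7 to 8.4 h (Protocol 1.1.2.2).

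| V-FU after V4 | Hours | At 8.4 h | At 5.7 h |
|---|---|---|---|
| 3 weeks | 504 | 60.0 | 88.4 |
| 4 weeks | 672 | 80.0 | 117.9 |
| 5 weeks | 840 | 100.0 | 147.4 |

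The strict minimum is 60; 80 to 118 is the nominal range.

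**Step 2: metabolite.** Less than 1% of the dose is excreted unchanged, and no half-life is given for IFB-139. If 24 to 48 h is assumed, 3 to 4 weeks is 504/48 = 10.5 to 672/24 = 28 half-lives. The conclusion does not change.

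**Step 3: treatment time after the only on-treatment sample.** (26 − 4)/26 = 22/26 = 84.6%. With ± 4 days on each visit, V2 falls on day 24 to 32 and V4 on day 178 to 186. The share is then (178 − 32)/178 = 82.0% to (186 − 24)/186 = 87.1%.

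**Step 4: what other urine and blood tests cover.** Between weeks 4 and 26 the protocol schedules:

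- creatinine and eGFR at months 2, 4 and 5;
- renal panels, dipstick, quantitative urine protein markers and cytobacteriological examination at V3 and V4.

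The first three kinds of test measure function, blood and protein. The protocol does not say whether the cytobacteriological examination reports crystals, and it sets up crystalluria as a separate central-laboratory test.

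**Step 5: illustration of a V4 sample.** Assume that a share q of 28 active patients have crystals that first appear after week 4, and that one V4 sample shows them with probability s. The chance of at least one positive patient is 1 − (1 − qs)^28.

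| q | s = 0.25 | s = 0.5 | s = 1 |
|---|---|---|---|
| 5% | 29.7% | 50.8% | 76.2% |
| 10% | 50.8% | 76.2% | 94.8% |
| 20% | 76.2% | 94.8% | 99.8% |

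Under the current schedule the chance from dedicated microscopy in completers is about zero, if such crystals have cleared by V-FU. Both q and s are assumptions; the documents give neither.

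**The case against.** The best case for the plan is that week 4 is a reasoned choice. With this half-life, steady state is reached within days, and the pharmacokinetics were stable over 14 days. The rat toxicity was thought, from a 4-week study, to follow peak concentration more than total exposure. Dogs, studied for up to 39 weeks, showed no crystal nephropathy, and the protocol judges the rat finding likely to be species-specific. Renal toxicity itself is followed throughout by blood and urine tests, and safety is reviewed by the data and safety monitoring board. This makes V2 a sensible first sample and lowers the priority of the point. It does not explain why the second sample is taken off drug, where it adds little to the stated purpose.

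A reader might infer several stronger points that the documents do not support:

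- **That crystals in weeks 4 to 26 cannot be found at all.** Patients who stop early have microscopy at the discontinuation visit, which has no minimum delay and may fall on or near drug. The content of the cytobacteriological examination is also not specified, so it can be neither counted on nor ruled out.
- **That V-FU is useless for reversibility.** A patient positive at V2 and negative at V-FU has shown clearance. V-FU fails only for crystals that first arise after week 4.
- **That crystalluria is itself an event of special interest.** The listed category is renal toxicities.
- **That the V4 examination needs no extra urine.** Protocol 4.2.2.3 requires biomarker urine to be taken at a different time point, and Table 3 gives crystalluria its own 50 ml central-laboratory sample.
- **That the trial will claim absence of crystals over 26 weeks.** No such statement is planned.

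The SAP listing is sorted by treatment group (SAP 5.3), so in a trial of 50 a reader could count by hand. On its own, the missing table is a minor reporting preference.

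**Conclusion.** The point holds for completers. They have one dedicated on-treatment crystal examination, at week 4, and 22 of 26 treatment weeks (85%; 82% to 87% with visit windows) follow it with none. The next examination is at least 60 parent-drug half-lives after the last intake. Early stoppers are a partial exception, because their visit may be close to the last dose or up to four weeks after it.

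This is a weakness in when a safety measurement is taken; the sections agree with each other. It rests on three things: the phase I half-life in healthy volunteers applying to patients, crystals not persisting for weeks after the drug has gone, and routine urinalysis not being relied on to report crystals. The documents do not show that late crystals are likely. They leave the question open, and the present schedule cannot answer it with dedicated microscopy in completers. The change is worth making because it is cheap.

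**What to change.** Take the second crystalluria sample at the existing V4 visit, while the patient is still on study drug. Collect and handle it as at V2: first-morning urine, 50 ml, frozen within 3 hours and read at the central laboratory, separately from the biomarker urine. It would replace the routine V-FU sample. V-FU can be kept as an off-drug check, for example for patients positive at V2 or V4.

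In the SAP, keep the listing and add a count of patients with crystals by arm and visit.

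**Cost.** No extra visit. One 50 ml sample with freezing and shipping at V4, and a container given to the patient beforehand, offset by the dropped V-FU sample. The number of routine microscopies is unchanged. The routine off-drug sample is lost if the examination is moved; if V-FU is kept for everyone, the cost is one more microscopy per patient.

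**If follow-up has already ended.** The protocol synopsis planned the last patient out for the third quarter of 2024, before the SAP date of 12 November 2024, so the schedule change may come too late for this trial. The SAP count is still feasible, and the report should state that on-treatment crystal data in completers come from week 4 only.

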4.2.2 Measurements of secondary and exploratory variables

4.2.2.1 *Efficacy assessment*

Efficacy assessment will be performed at baseline (V0), 3 months (V3) and 6 months (V4). It will consist of:

- ALSFRS-R score,
- ALS-MITOS score,
- King's College score,
- Assessment of respiratory function: SVC and ABG. Sniff test will be optional, performed in sites that have the equipment and resources to perform it.
- Bioelectrical Impedance analysis

The ALSFRS-R, which compared to ALSFRS includes also respiratory function, is the most widely used and validated rating instrument for monitoring the progression of disability in patients with ALS. It consists of a disease-specific questionnaire with 12 questions aimed at assessing functionality [\[30-32\]](#). Functional decline averages about one point per month in untreated patients [\[33\]](#).

The ALS-MITOS score is a more recent staging system composed by 4 key domains included in the ALSFRS-R (walking/self-care, swallowing, communicating and breathing). It is a validated tool for predicting long-term survival of ALS patients [\[34, 35\]](#).

The King's College score is based on the number of neurological regions affected and requirement for gastrostomy or non-invasive ventilation [\[36, 37\]](#). While ALS-MITOS staging has greater

resolution for late disease stage corresponding to functional impairment, King's College score is able to differentiate early to mid-disease better, making the two systems complementary [38].

The monitoring of respiratory function is achieved by the measurement of SVC, assessed by spirometry: the patient is asked to take a breath as deep as possible, make a tight seal around the device mouthpiece, and then exhale. In SVC assessment, exhalation is performed slowly. SVC is simple, easy to perform and convenient for serial measurements over a long time to evaluate disease progression [39]. Recently, SVC has been chosen more and more frequently over forced vital capacity (FVC) test in ALS clinical trials as it is easier to perform for the patient while providing equivalent information [40]. However, it can be difficult for bulbar-onset ALS patients who experience facial weakness. The sniff test is a simple, portable, inexpensive test that expects patients to inhale through their noses with one nostril occluded and a probe connected to a pressure transducer. This test is easy to perform also for patients with facial weaknesses [39].

ABG test measures the pH and the levels of oxygen and carbon dioxide in the blood from an artery. ABG is a sensitive and inexpensive tool for monitoring respiratory function in ALS patients, and turned out to correlate with FVC. ABG does not require patient collaboration and is not influenced by bulbar involvement [41]. Arterial blood samples will be drawn through radial arterial puncture into heparin - lithium Vacutainer polyethylene tubes and immediately analysed using blood gas analyser, routinely calibrated, as appropriate.

Bioelectrical Impedance analysis will be performed using the non-invasive device BIODY XPERT^{ZM}, commercialized by Aminogram. The device is maintained by the patient on his ankle, in seated position, during approximately one minute, during which various parameters are recorded and proceeded by a software. All sites will be trained by Aminogram prior to utilization of the device. Once trained, members of the study team will be allowed to train additional members.

4.2.2.2 *Pharmacokinetic assessment*

Blood sampling for PK assessment will be performed at the V2 visit. The day before V2 the patient will go on site to be administered the IMP at 20:00. If the patient cannot come to the hospital on the day before V2, he will take study treatment at home at the time requested by the site (see [Section 4.1.4](#)). The day of V2 the patient will be administered again the IMP at 08:00. The blood samples for PK will be collected in the morning of V2. Patients can, but are not forced to, spend the night at the site between these 2 drug administrations, upon agreement between both parties.

Venous blood samples (10 mL) for the determination of plasma concentrations of IFB-088 and its hydroxylated metabolite IFB-139 will be drawn by direct venipuncture or via an intravenous catheter into heparin - lithium Vacutainer polyethylene tubes (5x2mL). Samples will be collected at the following time points in the morning: pre-IMP dose, 1, 2, 4 and 6 hours post dose. The actual date and time of each blood sample collection will be recorded.

IFB-088 and IFB-139 concentrations will be measured within one week, using a validated high-performance liquid chromatography with tandem mass spectrometry (HPLC/MS-MS) method. After collection, plasma samples will be stored at -80°C pending analyses. Details of PK blood sample processing, storage and shipping procedures will be provided in the LPM provided by the sponsor.

4.2.2.3 *Biomarkers assessment*

Potential biomarkers known to be associated with the evolution of the disease and potentially modulated by IFB-088 treatment will be assessed before and during study treatment. Blood, urine

and CSF samples will be collected for this assessment (see [Table 3](#)). Further details on blood, urine and CSF sample processing, storage and shipping procedures will be provided in the LPM provided by the sponsor. Frozen samples will be kept in a biobank for further analyses (see [Section 4.2.2.5](#)).

Blood biomarkers

Blood will be collected in 2 different types of tubes to measure potential biomarkers in both plasma and whole blood (messenger RNA [mRNA], microRNA [miRNA]). Blood should be first drawn in Ethylenediaminetetraacetic acid (EDTA) tubes and then in PAXgene Blood RNA Tube, as described below.

Plasma

Blood for plasma biomarkers assessment will be collected at V0, V3 and V4 according to schedule of activities ([Sections 3.7](#) and [4.1](#)) in 2 tubes of 10 ml containing EDTA properly labelled with patient identification. After processing, plasma will be aliquoted in and stored at -80°C pending analyses. Samples will be stored at a facility designated by the sponsor. The following parameters will be analysed at a laboratory approved by the sponsor:

- NfL light chain: at baseline and 6 months,
- NfL heavy chain: at baseline and 6 months,
- TDP-43: at baseline and 6 months,
- Inflammation biomarkers (interleukin [IL]-6, tumour necrosis factor- α [TNF α], interferon γ [IFN γ], IL-1 β , IL-8, IL-10, monocyte chemoattractant protein-1 [MCP-1], nerve growth factor [NGF], brain-derived neurotrophic factor [BDNF], vascular endothelial growth factor [VEGF]), transforming growth factor beta [TGF β]: at baseline, 3 and 6 months,
- Oxidative stress biomarkers (reactive oxygen species): at baseline, 3 and 6 months.

Unused plasma aliquots will be kept in the biobank ([Section 4.2.2.5](#)) for potential further analyses.

Whole blood

For whole blood biomarkers assessment, blood will be drawn at V0 and V4 in PAXgene Blood RNA tubes. Tubes must be at room temperature prior to use and properly labelled with patient identification. The tube should be gently inverted 8 to 10 times and store at -80°C pending analyses. Samples will be stored at a facility designated by the sponsor and will be kept in a biobank ([Section 4.2.2.5](#)) for potential further analyses.

Urine biomarkers

Urine will be collected at V0 and V4.

Urine samples of 100 ml will be collected and stored in accordance with the Urine & Kidney Proteome Projects standards [\[42\]](#). Sampling for urine biomarkers and routine safety/crystalluria must be collected at different time points. After processing the urine will be aliquoted, properly labelled with patient identification and stored at -80°C pending analyses. Urine samples will be stored at a facility designated by the sponsor and will be kept in a biobank ([Section 4.2.2.5](#)) for potential further analyses.

Cerebrospinal fluid biomarkers

CSF will be collected at V0 and V4 in patients willing to undergo lumbar puncture unless they present any contraindication to CSF sampling. These contraindications include the presence of risk for increased or uncontrolled bleeding and/or risk of bleeding that if not managed optimally could place a participant at an increased risk for intraoperative or postoperative bleeding. These could include, but are not limited to, anatomical factors at or near the LP site (e.g., vascular abnormalities, neoplasms, or other abnormalities) and underlying disorders of the coagulation cascade, platelet function, or platelet count (e.g., hemophilia, Von Willebrand's disease, liver disease). They also include anticipated need, in the opinion of the Investigator, for administration of any antiplatelet or anticoagulant medication (e.g., clopidogrel) that cannot be safely continued or held for an LP procedure, if necessary, according to local or institutional guidelines and/or Investigator determination.

INR should be measured prior to CSF sampling.

Patients with contraindications to lumbar puncture can be included in the study but will not undergo CSF sampling.

Lumbar puncture will be performed by a clinician according to the site's usual practice. The CSF will be collected and then aliquoted and properly labelled with patient identification. The tubes will be snap frozen in liquid nitrogen and immediately stored at -80°C, pending analyses. CSF samples will be stored at a facility designated by the sponsor and will be kept in a biobank ([Section 4.2.2.5](#)) for potential further analyses.

4.2.2.4 *Quality of life assessment*

QoL will be assessed using the validated ALSAQ-40 questionnaire, specifically used to measure the subjective well-being of patients with ALS [\[43\]](#). ALSAQ-40 has psychometric robustness, and it provides an interpretable picture of the impact of the condition on the subjective functioning and well-being of patients on areas that are of concern to them. It provides scores for 5 areas of health state: physical mobility (10 items), activities of daily living and independence (10 items), eating and drinking (3 items), communication (10 items), and emotional reactions (10 items). The questionnaire must be completed by the patient. Patients need to tick the box which best describes his/her own experience or feelings. Patients should try to answer every question even though some may seem rather similar to others, or may not seem relevant to them. QoL will be assessed as the change in absolute value and percentage of ALSAQ- 40 between baseline and 6 months.

4.2.2.5 *Biobank*

Blood, urine and CSF samples will be stored at -80°C at a facility designated by the sponsor to measure biomarker candidates as needed. These samples will be kept for 5 years after final database lock for further analysis and then destroyed if unused.

